5.5 Discontinuation from Study Drug or Subject Withdrawal from Study

Subjects can request to be discontinued from participating in the study at any time for any reason including but not limited to disease progression or lack of response to treatment. The investigator may discontinue any subject's participation at any time for any reason, including but not limited to disease progression, lack of response to treatment, an AE, safety concerns, or failure to comply with the protocol.

Subjects will have study drug discontinued immediately if any of the following occur:

- Abnormal laboratory results or AEs that either meet the criteria of discontinuation of study drug, as stated in Section 6.2 or rule out safe continuation of study drug.
- Serious infection (e.g., sepsis) that cannot be adequately controlled by anti-infective treatment or would put the subject at risk for continued participation in the trial as determined by the investigator.
- Confirmed diagnosis of deep vein thrombosis, pulmonary embolus or noncardiac, non-neurologic arterial thrombosis.
- The investigator believes it is in the best interest of the subject.
- The subject requests withdrawal from the study.
- Inclusion or exclusion criteria violation was noted after the subject started the study drug, when continuation of the study drug would place the subject at risk.
- Introduction of prohibited medications or dosages when continuation of the study drug would place the subject at risk.
- Subject is non-compliant with TB prophylaxis (if applicable) or develops active TB at any time during the study.
- The subject becomes pregnant while on study drug.

- Any malignancy, except for a localized nonmelanoma skin cancer (NMSC) or a carcinoma in-situ of the cervix which can successfully be treated at its localization.
- The investigator determines the subject is significantly non-compliant with study procedures.
- Subject develops a gastrointestinal perforation (other than due to appendicitis or mechanical injury).
- The subject experiences a serious hypersensitivity reaction without an alternative etiology.
- At Week 52, subject does not meet criteria for continuation into Period 2.

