5.6 Follow-Up for Study Drug Discontinuation or Subject Withdrawal from Study

Discontinuation of Study Drug and Continuation of Study Participation

Following discontinuation of study drug, the subject should be treated in accordance with the investigator's best clinical judgment, irrespective of whether or not the subject decides to continue participation in the study.

If a subject prematurely discontinues study drug, the procedures outlined for the Premature Discontinuation Visit (PD Visit) should be completed as soon as possible, preferably within 2 weeks, and preferably prior to initiation of another therapy. In addition, a 30-Day Follow-up Visit after the last dose of study drug is required to ensure all treatment-emergent AEs/serious adverse events (SAEs) have been

resolved. The Follow-Up Visit is not applicable for subjects who discontinued study drug and continued study participation and completed at least 1 study visit at least 30 days after last dose of study drug.

To minimize missing data for efficacy and safety assessments, subjects who prematurely discontinue study drug treatment should continue to be followed for all regularly scheduled visits for the period from which they discontinue as outlined in the Activity Schedule (Appendix D), unless subjects have decided to discontinue the study participation entirely (withdrawal of informed consent). That is, subjects who discontinue study drug during Period 1 should continue to follow the visit schedule for the remainder of Period 1, but not continue into Period 2. Subjects who discontinue study drug during Period 2, should follow the visit schedule for the remainder of Period 2. As noted in the Activity Schedule (Appendix D), at the visits after study drug discontinuation, subjects should adhere to all study procedures except for dispensing study drug or reviewing returns and accountability, dispensing/reviewing study drug instructions, dosing diaries, pharmacokinetic sample collection, and sample collection for exploratory research. Subjects should be advised on the continued scientific importance of their data even if they discontinue treatment with study drug early.

Premature Discontinuation of Study (Withdrawal of Informed Consent)

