7.2 Definition for Analysis Populations

The Full Analysis Set (FAS) will be defined for Period 1 and Period 2. The FAS population in Period 1 (FAS1) includes all randomized subjects who received at least 1 dose of study drug in Period 1. The FAS population in Period 2 (FAS2) is defined as all subjects who achieved remission for at least 24 consecutive weeks prior to the Week 52 Visit (at the end of Period 1) and received at least 1 dose of study drug in Period 2. In addition, an exploratory analysis set will be defined for Period 2 to include all subjects who did not meet these remission criteria (i.e., achieve remission for at least 24 weeks prior to the Week 52 Visit) but continued in Period 2 on their originally randomized treatment assignment. Primary efficacy analysis for primary and key secondary endpoints will be carried out on the FAS1 population in Period 1 and on the FAS2 population in Period 2. Exploratory efficacy analyses for Period 2 will be conducted for selected variables for the exploratory analysis set. Subjects will be grouped according to treatment as randomized.

The Per-Protocol Analysis Set will be defined to represent a subset of the FAS1 subjects without any major protocol violations during the study which are expected to impact the primary endpoint. Subjects to be excluded from the Per-Protocol Population will be identified before the Week 52 database lock. The Per-Protocol Population will be used to analyze the primary efficacy endpoint in a sensitivity analysis. Additional analyses may be conducted on the Per-Protocol Analysis Set in order to evaluate the impact of major protocol violations.

The Safety Analysis Set will be defined for Period 1 and Period 2. The Safety Analysis Set in Period 1 will consist of all subjects who received at least 1 dose of study drug in Period 1. The Safety Analysis Set in Period 2 will consist of all subjects who received at least 1 dose of study drug in Period 2. For the Safety

Analysis Set, subjects are assigned to a treatment group based on the treatment actually received, regardless of the randomized treatment.

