7.4 Statistical Analyses for Safety

Safety analyses for Period 1 and Period 2 alone and long-term safety analyses for Period 1 and Period 2 combined will be carried out using the Safety Analysis Set in Period 1 (for safety analyses for Period 1 alone and Periods 1 and 2 combined) as well as the Safety Analysis Set in Period 2 (for safety analyses for Period 2 alone) respectively, and will be based on treatments actually received regardless of the randomly assigned treatment.

Safety will be assessed by treatment-emergent adverse events (TEAEs), physical examination, laboratory assessments, ECG, and vital sign results. The number and percentage of subjects experiencing TEAEs by treatment group will be tabulated by the Medical Dictionary for Regulatory Activities (MedDRA) system organ class (SOC) and preferred term (PT). In addition, summaries of SAEs and TEAEs by severity and relationship to study drug as assessed by the investigator will be provided. SAEs, severe TEAEs, and TEAEs that lead to premature study discontinuation will be listed. Changes in vital signs, physical examination results, and clinical laboratory variables at each visit as compared to baseline will be summarized. Shift of laboratory values from baseline to defined time points will be tabulated.

Missing safety data will not be imputed.

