4.0 Analysis Populations

The following population sets will be used for the analyses.

- The Full Analysis Set (FAS) will be defined for Period 1 and Period 2.
 - The FAS in Period 1 (FAS1) consists of all randomized subjects who received at least 1 dose of study drug in Period 1.
 - The FAS in Period 2 (FAS2) consists of all subjects who achieved remission for at least 24 consecutive weeks prior to the Week 52 Visit (at the end of Period 1) and received at least 1 dose of study drug in Period 2.
- An exploratory analysis set (FAS2 E) is defined for Period 2 to include all subjects who had absence of GCA signs and symptoms AND were CS-free at the Week 52 visit, but did not achieve remission for at least 24 consecutive weeks prior to the Week 52 Visit, and continued and received at least 1 dose of study drug in Period 2 on their originally randomized treatment assignment.
- The Per-Protocol Analysis Set is defined to represent a subset of the FAS1 subjects without any major protocol violations during the study which are expected to impact the primary endpoint. The final criteria and the exclusion of subjects for the Per-Protocol Analysis Set will be finalized before the database lock for Primary Analysis. The Per-Protocol Analysis Set will be used to analyze the primary efficacy endpoint as a supplementary analysis.
- The Safety Analysis Set in Period 1 (SS1) consists of all subjects who received at least 1 dose of study drug in Period 1.
- The Safety Analysis Set in Period 2 (SS2) consists of all subjects who received at least 1 dose of study drug in Period 2.
- The Long-Term Safety Analysis Set (SS LT) consists of all subjects who received at least one dose of study drug in Period 1 and received the same study drug in Period 2.

Primary efficacy analysis for primary and multiplicity-controlled secondary endpoints will be carried out on FAS1 and SS1 (for the endpoint of rate of CS-related AEs) in Period 1. Efficacy analysis for additional endpoints in Period 1 will be carried out on FAS1, and efficacy analysis for additional endpoints in Period 2 will be carried out on FAS2.

Exploratory efficacy analyses for Period 2 will be conducted for additional endpoints in Period 2 on FAS2 E. For all efficacy analyses, subjects will be grouped according to treatment (or treatment sequence) as randomized.

For Safety Analysis Sets, subjects are assigned to a treatment group based on the treatment actually received, regardless of the treatment randomized.

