6.0 Study Treatment Duration and Compliance

Duration of treatment will be summarized for each treatment group on SS1 for Period 1, SS2 for Period 2 and SS LT across Period 1 and Period 2.

Duration of treatment will be summarized using the number of subjects treated, mean, standard deviation, median, minimum and maximum.

Study Drug Duration (in Days) in Period 1:

• Date of last dose of study drug in Period 1 Date of first dose of study drug in Period 1 + 1

Study Drug Duration (in Days) in Period 2:

• Date of last dose of study drug in Period 2 Date of first dose of study drug in Period 2 + 1

Study Drug Duration (in Days) for SS LT:

• Date of last dose of study drug - Date of first dose of study drug + 1

In addition, the number and percentage of subjects exposed to study drug will be summarized for the following cumulative duration intervals for SS1 and SS LT.

- $\geq 1 \text{ day}$
- ≥ 2 weeks
- \bullet > 4 weeks
- ≥ 12 weeks
- \geq 24 weeks

- \bullet > 36 weeks
- \geq 48 weeks
- \geq 60 weeks
- \geq 72 weeks
- \geq 84 weeks
- > 96 weeks

Treatment compliance will be summarized for each treatment group on SS1 for Period 1, SS2 for Period 2, and SS LT across Period 1 and Period 2. Treatment compliance is defined as the number of tablets actually taken divided by the number of tablets that should have been taken. Percent compliance will be summarized.

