10.2.1 Treatment-Emergent Adverse Events

Unless noted otherwise, all summaries included treatment-emergent AEs (TEAEs) only. TEAEs are defined as any event that begins or worsens in severity after initiation of study drug through 30 days post-study drug dosing. Events where the onset date is the same as the study treatment start date are assumed to be treatment-emergent. All treatment-emergent AEs will be summarized overall, as well as by primary MedDRA SOC and Preferred Term. The SOCs will be presented in alphabetical order, and the PTs will be presented in alphabetical order within each SOC.

The number and percentage of subjects experiencing treatment-emergent AEs will be summarized.

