10.2.4 Treatment-Emergent Adverse Events per Patient-Years of Exposure

Exposure-adjusted TEAEs per 100 patient-years will be provided, where TEAEs per 100 patient-years of exposure are defined as the number of TEAEs divided by the total exposure in 100 patient-years. The study drug exposure is defined as the last dose date minus the first dose date plus 30 days. Exposure-adjusted TEAEs will be summarized on SS1 for Period 1 and SS LT for long-term. Treatment differences between each upadacitinib dose group versus the placebo group together with 95% CI may also be provided on SS1 for Period 1 and SS LT for the long-term.

The exposure-adjusted incidence rate (EAIR) (censored at the time of first event) may be conducted for selected AESI endpoints as appropriate on SS LT for long-term.

10.2.5 Deaths, Serious Adverse Events, and Adverse Events Leading to Study Treatment Discontinuation

Treatment-emergent serious adverse events (SAEs), TEAEs leading to premature discontinuation of study treatment, and TEAEs leading to death will be summarized by SOC and PT.

Tabular listings will be provided for all deaths, all SAEs, Treatment Emergent SAEs, TEAEs leading to death, TEAEs leading to premature discontinuation of study treatment.

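### SAP 4.0 restricts the long-term safety set (SS LT) to same-drug continuers, against Protocol 7.4, so its rates and curves read low for AESIs that force study drug to stop in Period 1

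*SAP*

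**What the plan says.** The two documents name different populations for the same analysis.

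- **Protocol 7.4** assigns the combined-period safety analysis to the "Safety Analysis Set in Period 1 (for safety analyses for Period 1 alone and Periods 1 and 2 combined"). Protocol 7.2 defines that set without any Period 2 condition: "The Safety Analysis Set in Period 1 will consist of all subjects who received at least 1 dose of study drug in Period 1".
- **SAP 4.0** creates SS LT for the across-period analysis: "all subjects who received at least one dose of study drug in Period 1 and received the same study drug in Period 2". The version history in SAP 13.0 records that the set was added and says no more.

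Three other provisions determine the consequence.

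- **Who can enter Period 2.** Under Protocol 5.6, a subject who stops study drug in Period 1 follows the "visit schedule for the remainder of Period 1, but not continue into Period 2".
- **Which events force a stop.** Protocol 5.5 lists "Confirmed diagnosis of deep vein thrombosis, pulmonary embolus or noncardiac, non-neurologic arterial thrombosis", malignancy (except localized non-melanoma skin cancer or cervical carcinoma in situ that can be treated locally), gastrointestinal perforation (except from appendicitis or mechanical injury), and active tuberculosis. All are AESIs in SAP 10.2.6.
- **How time is counted.** SS LT duration in SAP 6.0 is "Date of last dose of study drug - Date of first dose of study drug + 1". For event rates, SAP 10.2.4 states: "The study drug exposure is defined as the last dose date minus the first dose date plus 30 days". Both start at the first Period 1 dose.

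SAP 10.2.4 and 10.2.6 then use SS LT for long-term exposure-adjusted rates of treatment-emergent events and AESIs, and for AESI Kaplan-Meier curves. Differences from placebo and incidence rates censored at first event are optional on this set.

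**The concern.** Membership of SS LT depends on something that happens after follow-up begins: reaching Week 52 on study drug and taking the same drug in Period 2. For an event that ends study drug, a Period 1 occurrence removes the subject, both the event and the time. Those who remain each contribute about a year in which such an event could hardly have been counted. This is immortal time.

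The affected outputs would appear beside the Period 1 results. For a mandatory-stop AESI, a reader would see a lower rate over two years than over one, even if the underlying risk never changed, and could take this as reassurance about longer exposure. Protocol 2.2 itself names thrombosis and malignancy among the concerns with JAK inhibition, and most of these events force a stop.

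**Working it through.** The plan states no figure for this point, so there is none to reproduce. The direction of the bias follows from the definitions. Its size needs assumptions.

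**Inputs from the documents.** Period 1 and Period 2 each last 52 weeks, taken as 1 year (Protocol 4.1). Membership and exposure are as in SAP 4.0, 6.0 and 10.2.4.

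**Assumptions, not in the documents.** Constant hazard L = 0.02 per year (2.0 per 100 patient-years); every event ends study drug; f = 1 year of Period 2 follow-up; the 30-day tail is ignored at first.

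**SS LT as written.** Per member:
- Events = 1 − exp(−L·f) = 1 − exp(−0.02) = 0.0198
- Person-years = 1 + (1 − exp(−L·f))/L = 1 + 0.990 = 1.990
- Rate = 0.0198/1.990 = 0.00995, about 1.0 per 100 patient-years, or 0.498 of the true rate

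**Everyone dosed in Period 1, time on the original drug.** With S = exp(−L) and a share c of those still on drug continuing it:
- Events = (1 − S) + c·S·(1 − S)
- Person-years = [(1 − S) + c·S·(1 − S)]/L
- Rate = L = 2.0 per 100 patient-years for any c

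Under a constant hazard, losing switchers and Week 52 non-qualifiers therefore does not itself distort the rate. The distortion comes from conditioning on no Period 1 stop.

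**Two-year cumulative incidence.** True: 1 − exp(−0.04) = 3.92%. SS LT: 1 − exp(−0.02) = 1.98%.

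**Variations**
- *Half of the events end study drug* (0.01 stopping, 0.01 not): the stopping part reads 0.00995/1.995 = 0.00499 and the other part is unbiased at 0.01. The total is 0.0150, or 1.5 per 100 patient-years.
- *30-day window* ("begins or worsens in severity after initiation of study drug through 30 days post-study drug dosing", with 30 days added to exposure): the ratio is 0.517 in place of 0.498.
- *Shorter Period 2 follow-up*, as at the Primary Analysis cut-off in SAP 2.2: the ratio is about f/(1 + f). For an assumed f = 0.85 it is 0.85/1.85 = 0.46.

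**Contrasts with placebo.** Assumed true rates are 2.0 and 1.0 per 100 patient-years, so the true difference is 1.0 and the true ratio 2.0.

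| Period 2 follow-up, upadacitinib / placebo (years) | SS LT rates per 100 PY | Difference | Ratio |
|---|---|---|---|
| 1 / 1 | 0.995 / 0.499 | 0.50 | 2.00 |
| 0.95 / 0.80 | 0.970 / 0.443 | 0.53 | 2.19 |
| 0.80 / 0.95 | 0.885 / 0.486 | 0.40 | 1.82 |

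With equal follow-up the difference is roughly halved and the ratio roughly kept. With unequal follow-up neither holds.

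**The case against.** The strongest reply is that the report as a whole does not lose these events. The Period 1 safety set (SS1) is everyone dosed in Period 1. It carries the adverse event overview with differences from placebo, exposure-adjusted rates and AESI curves. The listings of deaths and serious adverse events in SAP 10.2.5 are not tied to SS LT. All of this stands. A reader might infer that Period 1 thromboses or cancers vanish, or that the randomized safety comparison is compromised; the documents do not support either. But SS1 covers only Period 1 and does not correct a two-year rate.

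Second, the reach is limited. Protocol 6.2 allows continuation or restart for most other AESIs, including treated serious infection, herpes zoster, non-fatal MACE and most laboratory abnormalities. To read the whole AESI list as halved would be wrong: those events are affected only when a subject actually stops.

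Third, a reader might conclude that SS LT curves for mandatory-stop events must be flat through Week 52. That is too strong. SAP 7.3 plans a deviation category for subjects who met withdrawal criteria and were not withdrawn, and their events can be counted. So can events confirmed only after Period 2 dosing starts.

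Fourth, SAP 6.0 tabulates SS LT exposure in bands from 1 day upward, which say little if every member has reached Period 2. A wider set may have been intended. The list is shared with SS1, however, and the definition as written is restrictive, so the text needs correcting on either reading.

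Finally, a same-drug set keeps upadacitinib and placebo time apart after re-randomization, and Protocol 7.4 gives no rule for that. This is a legitimate aim, but ending follow-up by drug received achieves it without removing Period 1 stoppers.

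**Conclusion.** The point holds for the SS LT outputs. SAP 4.0 departs from Protocol 7.4, neither document explains why, and the departure biases SS LT exposure-adjusted rates and AESI Kaplan-Meier curves downward for events that end study drug in Period 1. The direction does not depend on the assumed hazard.

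The size does. A halving, 2.0 read as about 1.0 per 100 patient-years, applies to a constant hazard, an event that always ends study drug and a full year of Period 2 follow-up. It is about a quarter if half of the events end study drug. The documents give no AESI rates, so these are illustrations and not forecasts.

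One might infer that differences from placebo always shrink by the same factor, or that the bias always favours upadacitinib. Neither follows. The effect on a contrast depends on follow-up and stopping in each arm, and SS LT differences are optional in any case. The primary and other efficacy analyses are untouched. The definition should be corrected before the long-term outputs are produced.

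**What to change.** In SAP 4.0, define the long-term set as all subjects dosed in Period 1, which is the Protocol 7.4 population, grouped by Period 1 treatment received.

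- **Follow-up.** Count events and person-time from first dose to last dose of the Period 1 treatment plus 30 days. Align SAP 6.0, 10.2.1 and 10.2.4 so that, for this set, last dose means the last dose of that treatment.
- **Switchers.** Apply the same rule to subjects re-randomized from upadacitinib to placebo. Events and time up to 30 days after the last upadacitinib dose go to upadacitinib; later events and time are excluded from this analysis. This is an addition, because Protocol 7.4 has no rule for switchers.
- **Continuers.** Keep same-drug continuers only as a subset labelled as such.
- **Footnote.** State that Year 2 time comes only from subjects who met the Week 52 continuation criteria, so Year 2 contrasts with placebo are not randomized comparisons. The new definition does not remove that limit.

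The cost is one definition, one attribution rule to program and one footnote, with no new data. Long-term rates may look less favourable.

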5.0 Subject Disposition

Enrollment failure subjects and the associated reasons for failure to randomize will be tabulated for all screened subjects.

[figure not shown]
Separately for Period 1 and Period 2, the number and percentage of subjects for each of the following categories will be summarized, for overall and for each treatment group (or treatment sequence) on FAS1 and FAS2:

- Subjects randomized in the study
- Subjects who took at least one dose of study treatment
- Subjects who completed study treatment
- Subjects who prematurely discontinued study treatment
- Subjects who completed study participation
- Subjects who prematurely discontinued study participation

Primary reason and all reasons for premature discontinuation of study drug and study participation will be summarized separately by treatment group and overall, with frequencies and percentages by reason for discontinuation.

The subject disposition for Period 1 will be summarized overall and by randomized treatment group in Period 1.

The subject disposition for Period 2 will be summarized overall and by each treatment sequence on FAS2 and FAS2 E.

In addition, a summary of subject accountability by investigator will be provided for Period 1, where the number of subjects in each of the above categories will be tabulated for each treatment group on FAS1.

